6.16 Appropriateness of Measurements

PGD3 at T72 and 30-day mortality are the primary safety endpoints measured for subjects in this study (Section 2.1).

PGD3 has been shown in the literature to be a very good predictor of transplanted organ function as it has a significant impact on short- and long-term recipient survival including:

- PGD3 at T72 demonstrated a significantly higher risk of 30-day mortality, accounting for 50% of all-cause deaths compared to PGD0 at T72.
- PGD3 at T72 is associated with an increased 90-day mortality rate of 18% and an increased 1-year mortality rate of 23%.
- PGD3 at T72 has the strongest association with long-term mortality compared to PGD scores at other time points post-transplant even after 1 year.[[Suzuki 2013](#)]

Over 100 lung transplants using lungs after undergoing EVLP at TGH and showed similar 30-day, 1-year, and 3-year survival outcomes compared to the contemporaneous (non-EVLP) recipient populations.[[[name] 2011a](#); [[name] 2011b](#); [[name] 2012](#); [Tikkanen 2012](#); [Munshi 2013](#); [[name] 2013](#)] Similarly, in this study, short-term and long-term survival will be documented for all subjects.

While the prognostic value of PGD grading in DLT has gained clinical acceptance, the experience with PGD scores in SLT is more limited. In DLT, the measurement of oxygenation reflects the contribution of both transplanted lungs. In contrast, measured oxygenation reflects contributions from both a diseased, native lung and a transplanted graft when only a single lung is transplanted. The Lung Transplant Outcomes Group found the SLT itself was a risk factor for adverse PGD scores and was associated with worse long-term outcomes [[Diamond 2013](#)], although the reasons for this association are not understood. Thus, to address the lack of clinical clarity, the measurement of 30-day mortality is included as a co-primary endpoint, and is intended to account for the uncertainty provided by PGD scoring of SLT. Both co-primary endpoints will be considered to inform on prediction of long-term survival in SLT recipients. The contemporaneous control group will be used to provide context for interpreting these results.

7 STUDY ACTIVITIES

A review of the transplant candidate files, donor information, and lung evaluation is required to determine preliminary eligibility according to recipient and donor lung inclusion and exclusion criteria.

The Study Schedule of Events is tabulated in [Appendix 1](#) for both the Analysis Phase (Table 3) and the Long-term Follow-up Phase (Table 4).

7.1 Screening Visit (Days –365 to -1 [-24 hours])

A Screening Visit may occur any time from up to one year to the day of lung transplant. The following may be conducted during this visit:

- Obtain informed consent per Section 10.4.
- Determine patient eligibility according to applicable Inclusion (Section 4.2) and Exclusion Criteria (Section 4.3).

7.2 Intervention

7.2.1 Lung Assessment, Recipient Baseline, and Lung Transplant (Day 0)

7.2.1.1 Donor Lung Screening (Day 0, within 24 hours prior to transplant)

For EVLP lung donors, the Sponsor will perform the following:

- Collect donor information (see Section 6.1)
- Confirm donor lung eligibility according to the donor Inclusion (Section 5.2.1) and Exclusion criteria (Section 5.2.2) for EVLP Assessment.

For Control subjects, the Investigator will perform the following:

- Collect donor information (see Section 6.1)
- Forward donor information for entry into Sponsor CRF

7.2.1.2 Recipient Screening (Day 0, within 24 hours before transplant)

For both EVLP and Control subjects, the Investigator will perform the following:

- Consent or reconfirm consent in accordance with the IRB policy.
- Collect the following recipient information:
 - Medical history of diseases or conditions ongoing in the past year.
 - Date of Birth

- Gender
 - Ethnicity
 - Race
 - Weight
 - Height
 - LASDDG
 - LAS
 - Oxygen requirement status (L/min)
- Perform physical examination.
 - Confirm recipient eligibility in accordance with the recipient Inclusion (Section 4.2) and Exclusion Criteria (Section 4.3).

7.2.1.3 Donor Lung EVLP Evaluation (at completion)

The Sponsor will perform the following:

- Record preservation information (see Section 6.1): cross clamp time/ start of first cold preservation (CIT-1), volume, type, macroscopic lung evaluation.
- Confirm donor lung eligibility in accordance with the donor lung Inclusion (Section 5.2.3.1) for transplant suitability AFTER EVLP.
- Clinical parameters will be collected and used as part of the EVLP suitability evaluation that is performed by the Investigator.

7.2.1.4 Lung Transplantation (Day 0)

Provided all recipient and lung Inclusion and Exclusion Criteria have been met, the Investigator or his/her designee will record the following at the time of admission to the ICU after lung transplantation:

- Hospital admission date
- Transplant date and time, including removal from cold storage time for each lung
- ICU admission time and date
- Initial PaO₂ and FiO₂ upon ICU admission
- PGD score (0 hrs)

7.3 Post-intervention Period; Analysis Phase (Day 1 to 1 Year Post-Transplant)

7.3.1 Visit 1 Procedures (24 Hours post-transplant)

At 24-hrs post-transplant (\pm 4 hrs), the Investigator or his/her designee should perform the following:

- Record PGD Score (Section 6.7)

- Assess any AEs

7.3.2 Visit 2 Procedures (48 Hours post-transplant)

At 48-hrs post-transplant (\pm 8 hrs), the Investigator or his/her designee should perform the following:

- Record PGD Score (Section 6.7)
- Assess any AEs

7.3.3 Visit 3 Procedures (72 Hours post-transplant)

At 72-hrs post-transplant (\pm 12 hrs), the Investigator or his/her designee should perform the following:

- Record PGD Score (Section 6.7)
- Record extubation date/time (if applicable)
- Record ICU discharge time/date (if applicable)
- Assess AEs

7.3.4 Visit 4 Procedures (Day 30 post-transplant)

On Day 30 post-transplant (\pm 5 days), the Investigator or his/her designee should record the following:

- Subject and graft survival and if failed, cause of failure
- If extubated >72 hrs post-transplant, extubation time
- FEV₁ (Day 30 or upon hospital discharge, if before 30 days)
- Oxygen required at rest (Day 30 or upon hospital discharge, if before 30 days)
- Hospital discharge date and readmission date(s) (if applicable)
- Assess AEs

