6.5 Physical Examination

Physical examination(s) should be performed by the Study Center for all patients as a standard of practice prior to listing patient for transplantation.

A physical examination should be performed at the Baseline Visit. Symptom-directed physical examinations will be performed again at Day 30 and Month 6 post-transplant. Any values judged by the Investigator to be clinically significant abnormal changes from Baseline (before study intervention) should also be recorded on the Adverse Event CRF as an AE.

Specific tests to assess lung capacity will also be obtained and recorded on the CRF. Upon admission to the ICU, the subject's initial PaO₂ is to be recorded.

FEV₁, measured as a percentage of predicted normal value, and oxygen required at rest are to be recorded at the time of hospital discharge (if prior to 30 days post-transplant), Day 30, Day 90, Month 6, and Year 1 post-transplant, and premature discontinuation (if applicable).

In addition, after completion of the Analysis Phase, FEV₁ and oxygen at rest will be collected annually by the Sponsor for the Long-term Follow-up Phase (Year 2, 3, 4, and 5).

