9.7 Exploratory Endpoints

Other safety endpoints that will be analyzed include:

- Initial ICU PaO₂: Evaluated as first PaO₂ measured after ICU admission.
- FEV₁: Evaluated at time of discharge, 30 days, 90 days, 6 months and 1 year post-transplant. FEV₁ is measured as a percentage of predicted normal value.

- Oxygen Requirement at Rest: Evaluated at time of discharge, 30 days, 90 days, 6 months and 1 year post-transplant.
- Subject Survival: Evaluated at 90 days, 6 months and 1 year post-transplant. Measured as living or dead. If the subject expires within first year post-transplant, the date of death and primary cause of death will be collected.
- Graft Survival: Evaluated at 30 days, 90 days, 6 months and 1 year post-transplant. Measured as functioning or failed. If the graft fails within first year post-transplant, the date of graft failure will be collected.
- Primary Cause of Graft Failure: Evaluated at 30 days, 90 days, 6 months and 1 year post-transplant on all failed grafts.
- Bronchiolitis Obliterans Syndrome (BOS) Grade: Evaluated at 90 days 6 months and 1 year post-transplant.
- Number of Re-hospitalizations after Transplant: Evaluated at 6 months and 1 year post-transplant. Measured as total number of hospitalizations since initial discharge.
- Physical Capacity: Evaluated at 90 days, 6 months and 1 year post-transplant.
- Working for Income after Transplant: Evaluated at 90 days, 6 months and 1 year post-transplant.

All exploratory endpoints will be presented using descriptive statistics along with two sided 95% CIs by Transplant Group. Other supportive endpoints may be included as needed.

Results may be displayed graphically. There will be no inferential testing conducted.

In addition, supplemental analyses comparing the EVLP group and the Control Group may be performed to provide context of results observed in this study (details will be described in the SAP).

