4.3 Assessment Windows

For the purpose of analyzing time to event endpoints, the time-in-study for each patient will be measured relative to Day 0, the day of transplantation.

For the purpose of listing and summarizing data, the time-in-study for each patient observation will be defined using study days. Such days will be measured relative to Day 0, the day of transplantation.

All data will be summarized by visit based on the visit in which the data was recorded in the database.

Baseline will be defined as the last pre-intervention value during the screening period. If more than one assessment exists within a single visit window, the value closest to the protocol study visit will be used for summary and analysis purposes. Data from all assessments will be listed.

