6.3 Exploratory Endpoints and Analyses

Other safety endpoints that will be analyzed include:

- Initial ICU PaO₂: Evaluated as first PaO₂ measured after ICU admission.
- FEV₁: Evaluated at time of discharge, 30 days, 90 days, 6 months and 1 year post-transplant. FEV₁ is measured as a percentage of predicted normal value. Oxygen Requirement at Rest: Evaluated at time of discharge, 30 days, 90 days, 6 months and 1 year post-transplant.
- Subject Survival: Evaluated at 90 days, 6 months and 1 year post-transplant. Measured as living or dead. If the subject expires within first year post-transplant, the date of death and primary cause of death will be collected.
- Graft Survival: Evaluated at 30 days, 90 days, 6 months and 1 year post-transplant. Measured as functioning or failed. If the graft fails within first year post-transplant, the date of graft failure will be collected.
- Primary Cause of Graft Failure: Evaluated at 30 days, 90 days, 6 months and 1 year posttransplant on all failed grafts.
- Bronchiolitis Obliterans Syndrome (BOS) Grade: Evaluated at 90 days 6 months and 1 year post-transplant.
- Number of Re-hospitalizations after Transplant: Evaluated at 6 months and 1 year post-transplant. Measured as total number of hospitalizations since initial discharge, the number of re-hospitalizations per subject, and whether the subject had a re-hospitalization related to transplant.
- Physical Capacity: Evaluated at 90 days, 6 months and 1 year post-transplant.
- Working for Income after Transplant: Evaluated at 90 days, 6 months and 1 year post-transplant.

Initial ICU PaO₂ and FEV₁ will be presented using descriptive statistics by Transplant Group. All other exploratory endpoints are categorical and will be summarized by presenting the number of subjects and percentage for each category. Other supportive endpoints may be included as needed.

Results may be displayed graphically. There will be no inferential testing conducted.

In addition, supplemental analyses comparing the EVLP group and the Control Group may be performed to provide context of results observed in this study.

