10. APPENDICES

10.1 Appendix A: Schedule of Events

Schedule of Events Within 1 Year Post-Intervention

Evaluation	Screening Days -365 to 0	Baseline; Day 0	Post-Intervention Period							Follow-up
			Visit 1 (ICU); 24hr ± 4	Visit 2 (ICU); 48hr ± 8	Visit 3 (ICU); 72hr ± 12	Visit 4; Day 30 ± 5	Visit 5; Day 90 ± 10	Visit 6; 6 mon ± 2wks	Visit 7; 1 year ± 4 wks	Premature Discot'n
Signed Informed Consent ^b	X	X	-	-	-	-	-	-	-	-
I/E Criteria	X	X ^a	-	-	-	-	-	-	-	-
Print conmeds source		X ^a	-	-	-	X	-	-	X	-
Donor data collection ^c (Sponsor responsibility)	-	X	-	-	-	-	-	-	-	-
EVLP data collection ^d (Sponsor responsibility)	-	X	-	-	-	-	-	-	-	-
Demographics and Baseline Disease Characteristics	X	X ^a	-	-	-	-	-	-	-	-
Medical History	X	X ^a	-	-	-	-	-	-	-	-
Study intervention (lung transplant)	-	X	-	-	-	-	-	-	-	-
Post-transplant Assessments (Study Investigator)										
Vital sign assessments	X	X	X	X	X	X	X	X	X	X
Physical Examination	-	X ^a	-	-	-	X	-	X	-	-
PGD Score (Section 6.7)	-	X	X	X	X	-	-	-	-	-
PaO ₂ and FiO ₂	-	X	-	-	-	-	-	-	-	-
Pulmonary function tests						X ^e	X	X	X	(X)
FEV ₁	-	-	-	-	-	X ^e	X	X	X	(X)
Oxygen at rest	-	-	-	-	-	X ^e	X	X	X	(X)
BOS Grade	-	-	-	-	-	-	X	X	X	(X)
ICU discharge	-	-	-	-	(X)	(X)	-	-	-	(X)
Extubation date/time	-	-	-	-	(X)	(X)	-	-	-	(X)
Hospital discharge	-	-	-	-	(X)	(X)	-	-	-	(X)
Hospital readmission	-	-	-	-	-	(X)	(X)	(X)	(X)	(X)
Physical capacity	-	-	-	-	-	-	X	X	X	(X)
Work status	-	-	-	-	-	-	X	X	X	(X)
Adverse event assessment	-	X	(X)	(X)	(X)	(X)	(X)	(X)	(X)	(X)

Graft Survival Assessment	-	-	-	-	-	X	X	X	X	(X)
Survival Assessment	-	-	-	-	-	X	X	X	X	(X)

Abbreviations: BOS=bronchiolitis obliterans syndrome; conmed=concomitant medications; discont'n=discontinuation; FEV₁=forced expiratory volume in one minute; hrs=hours; ICU=intensive care unit; I/E=inclusion/exclusion; mon=month; PaO₂=partial pressure of oxygen in arterial blood; primary graft dysfunction; wks=weeks

Note(s): (x)=indicates "if applicable or as appropriate"

^a Data at Baseline are to be collected within 24 hrs prior to lung transplant.

^b Informed consent must be provided by the subject up to one year in advance and confirmed up to 24 hrs in advance of the lung transplant if required (Section 10.4.1).

^c Collection of donor demographics and suitability data. Confirm donor lung inclusion/exclusion criteria (Section 5.2.1 and Section 5.2.2).

^d Collect EVLP case data to determine transplant suitability and lung inclusion/exclusion criteria (Section 5.2.3).

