^e At the time of discharge.

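### FEV1 and oxygen at rest are endpoints at both discharge and Day 30, but conflicting collection instructions and labelling by recorded visit could put discharge values under Day 30 or drop them from the summary

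*Protocol*

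**What the plan says.** **Endpoints.** Protocol 2.3 and 9.7 and SAP 2.1.3, 2.2.3 and 6.3 list discharge and 30 days as two time points for both measures. For FEV1, Protocol 9.7 has "Evaluated at time of discharge, 30 days, 90 days, 6 months and 1 year post-transplant". For oxygen, SAP 6.3 has "Oxygen Requirement at Rest: Evaluated at time of discharge, 30 days, 90 days, 6 months and 1 year post-transplant".

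**Collection.** Three places tell sites what to record:

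- Protocol 6.5 asks for FEV1 and oxygen at rest to be "recorded at the time of hospital discharge (if prior to 30 days post-transplant), Day 30, Day 90", and then at the later visits.
- Protocol 7.3.4, the Visit 4 instruction, qualifies both measures with "Day 30 or upon hospital discharge, if before 30 days".
- SAP Appendix A has a column headed "Visit 4; Day 30 ± 5" and none for discharge. The Visit 4 cells for pulmonary function tests, FEV1 and oxygen at rest carry a footnote that reads "At the time of discharge".

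**Analysis.** SAP 4.3 states: "All data will be summarized by visit based on the visit in which the data was recorded in the database". The same section says that when one visit window holds several assessments, the one nearest the protocol visit is summarised and all are listed. SAP 6.3 gives FEV1 continuous summary statistics and treats oxygen at rest as categorical, with counts and percentages.

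**The concern.** The endpoint lists promise two separate estimates. The collection instructions disagree on whether two values are taken, and the SAP has no rule that tells them apart. Lung function measured at discharge falls on a day set by length of stay, whereas Day 30 is a fixed time. If the two share a label, the Day 30 summary mixes early post-operative values with true Day 30 values, and the discharge row may be empty.

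The visit label carries much of the FEV1 analysis. The SAP revision table records that change from baseline in FEV1 was removed because values summarised at each visit were judged sufficient. The Control group is also meant to supply estimates for designing later studies, so a mislabelled Day 30 estimate could be carried forward.

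**Working it through.** The plan states no figure on this point to reproduce. The check sets the instructions side by side and follows a value through to the summary.

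**Step 1: what is collected from a subject discharged before Day 30**

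| Source | Discharge value | Day 30 value |
|---|---|---|
| Endpoint lists (Protocol 9.7, SAP 6.3) | expected | expected |
| Protocol 6.5 | required | required |
| Protocol 7.3.4 | either one satisfies the instruction | either one satisfies the instruction |
| SAP Appendix A | footnoted on the Visit 4 cell | no cell of its own |

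Protocol 6.5 agrees with the endpoint lists for these subjects; 7.3.4 and the schedule do not. The argument uses the SAP's copy of the schedule because the footnote letter in the protocol's copy is not clearly legible in the text available. A smaller gap is that 6.5 limits the discharge recording to discharge before 30 days, while the endpoint lists set no such limit.

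**Step 2: what SAP 4.3 does with the data**

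| What is entered | Summary result |
|---|---|
| Discharge and Day 30 values in separate records | Both labelled correctly |
| Only a discharge value, from Days 25–29, at Visit 4 | Valid as a Day 30 value; no separate discharge entry |
| Only a discharge value, from before Day 25, at Visit 4 | Labelled Day 30 although outside the window; no true Day 30 value |
| Both values at Visit 4, treated as one window | Day 30 value kept as the nearest; discharge value appears only in the listings |

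The boundary comes from the visit window: 30 − 5 = Day 25.

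**Step 3: size**

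Inputs: 66 subjects per group (Protocol 9.2). The share s discharged before Day 30 is not in the documents, so it is assumed over a range. Subjects per group = 66 × s.

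- s = 0.25: 66 × 0.25 = 16.5, about 17
- s = 0.50: 66 × 0.50 = 33
- s = 0.75: 66 × 0.75 = 49.5, about 50
- s = 0.90: 66 × 0.90 = 59.4, about 59

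For each assumed s, this is a ceiling on the number mislabelled. From it must be taken subjects discharged on Days 25–29, subjects whose sites recorded both values as 6.5 requires, and any whose discharge value sits in its own database record.

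**The case against.** The strongest reply is that the protocol already asks for the right data. Section 6.5 requires both recordings and SAP 6.3 lists both time points. If the database holds a discharge record, the recorded-visit rule in SAP 4.3 labels it correctly. The case report form is not among the documents, so this cannot be excluded. SAP 4.3 also lists every assessment and defines study days for each observation, and 7.3.4 records the discharge date, so a discharge value could be recognised in the listings. Where both values are entered under Visit 4 and treated as one window, the nearest-value rule protects the Day 30 summary. The endpoints are exploratory and descriptive, with no inferential testing.

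Most of this stands and limits the point to what could happen. It does not remove the contradiction between 6.5 and 7.3.4, nor does it supply a discharge analysis visit. The nearest-value rule protects Day 30 only by dropping discharge from the summary, and a listing does not correct a summary table.

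Two stronger readings are tempting. A reader might infer that every subject discharged before Day 30 will be misreported, with one of the two time points impossible to fill. Section 6.5 and the ±5-day window rule that out. A reader might also infer a bias between groups, because the mix of early and true Day 30 values depends on length of stay. Length of stay is a secondary endpoint, but no document says that it differs between EVLP and Control, so this is only a possibility.

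**Conclusion.** The inconsistency is real and minor. As written, 7.3.4, the schedule footnote and SAP 4.3 together allow a discharge value to be summarised as Day 30, or a discharge value to be lost from the summary. Mislabelling matters mainly for discharge before Day 25. It requires that the site takes only the discharge value, as 7.3.4 permits, that it enters the value at Visit 4, and that no separate discharge record exists.

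The number of subjects cannot be determined from the documents; the range above is illustrative. For FEV1 the effect would be on the mean and the other continuous summaries, and for oxygen at rest on the category counts. The two primary endpoints, Grade 3 primary graft dysfunction at 72 hours and 30-day mortality, are unaffected.

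**What to change.** **Protocol.** Align 7.3.4 and the schedule footnote with 6.5, so that discharge and Day 30 values are recorded separately, each with its assessment date. State whether the discharge endpoint applies to subjects discharged on or after Day 30.

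**SAP 4.3 and 6.3.** Define separate discharge and Day 30 analysis time points for FEV1 and oxygen at rest. Assign each value by its assessment date, relative to the discharge date and to the Day 30 ± 5 window, rather than by recorded visit. Say whether a discharge value from Days 25–29 may serve both time points. Report an unfilled time point as missing, and give the number of non-missing values at each.

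**Cost.** A wording correction, separate dated fields if the case report form lacks them, and one derivation rule. No measurement is added beyond what 6.5 already requires. Values already collected can be reassigned if their assessment dates were captured. The price is that some Day 30 cells may become missing where only an early discharge value exists.

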7.3.5 Visit 5 Procedures (Day 90 post-transplant)

On Day 90 post-transplant (\pm 10 days), the Investigator or his/her designee should record the following:

- Subject and graft survival and if failed, cause of failure
- FEV₁
- Oxygen required at rest
- BOS Grade
- Physical capacity

- Working for income status
- Hospital readmission date(s) (if applicable)
- Assess AEs

7.3.6 Visit 6 Procedures (Month 6 post-transplant)

At Month 6 post-transplant (± 2 weeks), the Investigator or his/her designee should record the following:

- Subject and graft survival and if failed, cause of failure
- FEV₁
- Oxygen required at rest
- BOS Grade
- Physical capacity
- Working for income status
- Hospital readmission date(s) (if applicable)
- Assess AEs

7.3.7 Visit 7 Procedures/ Final Visit (1 year post-transplant)

The final study visit for the Analysis Phase will occur one year post-transplant At Year 1 post-transplant (± 4 weeks), the Investigator or his/her designee should record the following:

- Subject and graft survival and if failed, cause of failure
- FEV₁
- Oxygen required at rest
- BOS Grade
- Physical capacity
- Working for income status
- Hospital readmission date/s (if applicable)
- Assess AEs

